2.1.3.2.3 Time to progression

The time to progression is defined as the time interval from the date of first study treatment administration to the date of first radiologically documented tumor progression or death from disease progression before the initiation of any post-treatment anti-cancer therapy, whichever occurs first.

If a patient receives post-treatment anti-cancer therapy before radiologic progression or death, TTP will be censored at the date of the last valid response assessment without evidence of progression performed before the initiation of the post-treatment anti-cancer therapy.

If death different from disease progression occurs before receiving post-treatment anti-cancer, TTP will be censored at the date of the last evaluable response assessment without progression.

If a patient receives post-treatment anti-cancer therapy without radiologic progression or death, TTP will be censored at the date of the post-treatment anti-cancer therapy.

In the absence of tumor progression or death due to disease progression or post-treatment anti-cancer therapy, TTP will be censored at the date of the last valid response assessment without evidence of progression. An evaluable response assessment is defined as a response assessment with a response different of NE.

2.1.3.2.4 Progression-free survival

Progression-Free Survival (PFS) is defined as the time interval from the date of the first treatment infusion to the first documented date of disease progression or death due to any cause, whichever occurs first.

Rules for sensitivity analysis

PFS endpoint will be determined considering also clinical/non radiological progression as an event. If clinical/non radiological progression is observed in absence of documented radiological progression, the date of progression will be the date of clinical/non radiological progression. If the first progression is based on documented radiological progression and on clinical/non radiological progression, the date of progression will be the earliest of date of documented progression and date of clinical/non radiological progression.

Censoring rules for all PFS analyses:

For these 2 analyses, in the absence of disease progression or death (or clinical/non radiological progression for sensitivity analysis), the PFS will be censored at the date of last evaluable tumor assessment without documented progression. In addition, the patient without any valid post-baseline tumor assessment will be censored for PFS on the day of the first study treatment infusion (Day 1).

The summarized description of these analyses is given in [Appendix F](#).

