9.2 SECONDARY ENDPOINTS

9.2.1 Secondary efficacy endpoints

- DCR defined as the proportion of patients with CR, PR, or SD using RECIST 1.1 lasting more than 3 months as BOR.
- DOR defined as the time from the date of the first documentation of objective tumor response (CR or PR) to the date of first radiological documentation of tumor progression using RECIST 1.1, or death (due to any cause), whichever comes first.
- PFS defined as the time interval between the date of first study treatment administration and the date of the first radiologically documented tumor progression using RECIST 1.1, or death (due to any cause), whichever comes first.
- TTP defined as the time interval from the date of first study treatment administration and the date of the first radiologically documented tumor progression using RECIST 1.1.

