Appendix F Description of primary and sensitivity analyses of PFS

Table 20 - PFS Primary analysis

Situation	Date of progression or censoring	Outcome
No baseline tumor assessments	Date of first treatment administration	Censored
Documented progression according to investigator	Earlier of: - Date of radiological assessment showing new lesion or progression of non-target lesion - Date of last radiological assessment of target lesions (if progression is based on increase in sum of target lesions)	Event
Death without documented progression according to investigator	Date of death	Event
Both documented progression according to investigator and death	Date of progression	Event
No documented progression according to investigator and no death	Date of last valid tumor assessment without evidence of progression	Censored
Symptomatic deterioration reported and no documented progression according to investigator and no death	Ignored	Ignored
Initiation of new anti-cancer treatment	Ignored	Ignored

Table 21 - PFS sensitivity analysis #1 (progression based on investigator's assessment of lesions, and including symptomatic deterioration)

Situation	Date of progression or censoring	Outcome
No baseline tumor assessments	Date of first treatment administration	Censored
Documented Progression (without symptomatic deterioration) according to the investigator	Earlier of: - Date of radiological assessment showing new lesion or progression of non-target lesion - Date of last radiological assessment of target lesions (if progression is based on increase in sum of target lesions)	Event
Death without documented progression and without symptomatic deterioration	Date of death	Event
Symptomatic deterioration reported with no documented progression according to investigator and no death	Date of symptomatic deterioration	Event
Symptomatic deterioration and documented progression according to the investigator regardless of death occurrence	Earlier of the date of symptomatic deterioration and date of progression	Event
Symptomatic deterioration and death with no documented progression according to the investigator	Date of symptomatic deterioration	Event
Documented progression according to the investigator and death with no symptomatic deterioration	Date of progression	Event
No progression according to the investigator, no death, and no symptomatic deterioration	Earlier of the date of last valid tumor assessment without evidence of progression and cut-off date	Censored

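### The Day 1 censoring sentence for PFS has no 'no event' condition, so read literally it censors deaths before the first scan that the PFS definition and Appendix F count as events

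*SAP*

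**What the plan says.** SAP 2.1.3.2.4 measures PFS from the first infusion to "the first documented date of disease progression or death due to any cause, whichever occurs first". Protocol 9.2.1 also ends its definition with "or death (due to any cause), whichever comes first". Neither requires a scan before a death can count.

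The SAP section then gives censoring rules for both the primary and the sensitivity PFS analysis, in two sentences:

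- The first is conditional: "in the absence of disease progression or death (or clinical/non radiological progression for sensitivity analysis), the PFS will be censored at" the last evaluable assessment without progression.
- The second, introduced as an addition, says that "the patient without any valid post-baseline tumor assessment will be censored for PFS on the day of the first study treatment infusion (Day 1". It states no condition on death or progression.

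The section refers to Appendix F for a summary of these analyses. Three rows of Table 20 (primary analysis) matter here:

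- "No baseline tumor assessments": censored at first administration.
- "Death without documented progression according to investigator": event at the date of death.
- "No documented progression according to investigator and no death": censored at the last valid assessment.

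Table 21 (sensitivity analysis) has the same first row. It counts "Death without documented progression and without symptomatic deterioration" as an event at the date of death. It also counts symptomatic deterioration as an event at its own date, whether or not the patient later dies.

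**The concern.** The text and the tables can give different outcomes for one patient. Someone who dies in week 4 with no scan is censored at Day 1 under the literal sentence, and is an event at week 4 under the definition and Table 20. A programmer could code either.

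The SAP expects such patients. Its response evaluable population (2.3.1.2) makes provision for early death without a post-baseline assessment, and Appendix B describes these cases separately when it assigns best overall response. These are the worst PFS outcomes. Censoring them at time zero removes them from every risk set, so the error could only favour the drug.

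The sensitivity analysis is exposed in a second way. It exists to count clinical progression, and protocol 9.1.2 recognises that imaging may not be obtainable in that situation. A patient with clinical progression and no valid scan would be censored at Day 1 by the literal sentence, although Table 21 counts an event.

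**Working it through.** The plan states no event count, power or expected value for PFS, so there is no figure to reproduce. The check is a comparison of the rules, followed by an illustration of size.

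**Rules side by side**

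| Patient | Literal Day 1 sentence | Definition and Appendix F |
|---|---|---|
| Dies before first scan | Censored, Day 1 | Event at death (Tables 20 and 21; at deterioration in Table 21 if that was reported) |
| Symptomatic deterioration, alive, no valid scan (sensitivity analysis) | Censored, Day 1 | Event at deterioration (Table 21) |
| Alive, no PFS event, baseline scan but no valid post-baseline scan | Censored, Day 1 | No matching row; the general rows use a last valid assessment, and no post-baseline one exists |
| No baseline scan | Not addressed | Censored at first administration |

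The first two lines are contradictions under the literal reading. The last two show that the Day 1 trigger differs between text and tables on any reading.

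**Size if the literal rule were used**

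Inputs: N = 29 at the selected dose (SAP 1.3.2), 20 in Part 2b, 14 per Part 1 arm; scans every 6 weeks (SAP 2.1.3.1); Kaplan-Meier on all treated patients (SAP 2.4.4.2.5). The number d of deaths without a valid scan is not given and is assumed to be 1 to 5. No other early censoring is assumed.

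Let S be the PFS of the other N − d patients at time t.

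- Deaths as events: PFS(t) = S × (N − d)/N.
- Deaths censored at Day 1: PFS(t) = S.
- Difference: S × d/N.

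Just before the first scan, if no other patient has yet had an event, S = 1 and the difference is d/N. Per death this is 1/29 = 3.4 points, 1/20 = 5.0 points and 1/14 = 7.1 points. These are upper values, because the difference shrinks in proportion to S.

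For N = 29, PFS at 6 weeks with S = 1:

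| d | Deaths as events | Censored at Day 1 |
|---|---|---|
| 1 | 28/29 = 96.6% | 100% |
| 2 | 27/29 = 93.1% | 100% |
| 3 | 26/29 = 89.7% | 100% |
| 4 | 25/29 = 86.2% | 100% |
| 5 | 24/29 = 82.8% | 100% |

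Six weeks is not a reporting time in the SAP; the earliest planned landmark is 3 months. There S must also be assumed:

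| S at 3 months | Deaths as events, d = 1 | Deaths as events, d = 5 | Censored at Day 1 |
|---|---|---|---|
| 30% | 29.0% | 24.8% | 30% |
| 40% | 38.6% | 33.1% | 40% |
| 50% | 48.3% | 41.4% | 50% |

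For the median, assume that the other patients follow an exponential curve with median 3 months and that the early deaths fall before the overall median. Solving S × (29 − d)/29 = 0.5 gives 3 × ln(2(29 − d)/29)/ln 2, which is 2.85 months for d = 1 and 2.18 months for d = 5, against 3.00 months under Day 1 censoring.

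**The case against.** The best defence is that the Day 1 sentence only supplies a fallback date. The sentence before it applies when there is no progression or death, and it censors at the last evaluable assessment. A patient with no valid post-baseline scan has no such post-baseline date, so the added sentence says which date to use for patients who are already being censored. On that reading early deaths remain events. Everything else supports this: the definition in the same section, protocol 9.2.1, both tables, and SAP 2.4.4.2.5, which lists death as an event type and summarises the time from last assessment to death in patients who died without progression.

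This stands as a plausible account of what was meant. A reader might infer from the literal sentence that the SAP does remove early deaths and that the reported PFS will be inflated. The documents do not support that: the bias arises only if the literal rule is programmed, and its size depends on a number of deaths that is not given.

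The defence does not remove the defect. The condition is not written into the sentence, whereas in the neighbouring time-to-progression section (2.1.3.2.3) each censoring sentence carries its own condition. The mismatch between a post-baseline trigger in the text and a baseline trigger in the tables remains on either reading.

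It is also fair to say that little hangs on PFS here. It is secondary, summarised with 80% intervals and without a planned test. It enters neither the dose-selection criteria nor the rule of 7 responses in 29. SAP 2.5.3 keeps non-evaluable patients in the response-rate denominator as non-responders.

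**Conclusion.** The point holds as an internal inconsistency that should be corrected before programming. As written, the Day 1 sentence conflicts with the PFS definition, protocol 9.2.1 and Tables 20 and 21 for deaths before the first scan and, in the sensitivity analysis, for clinical progression without a scan. The tables also use a different Day 1 trigger.

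The upward bias is conditional on the literal reading. Its size cannot be derived from the documents; the per-death figures assume that no other patient has had an event by the first scan, and the 3-month and median figures rest further on assumed PFS in the remaining patients. Conclusions on ORR are not affected.

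**What to change.** Replace the Day 1 sentence in SAP 2.1.3.2.4 with wording such as: *A patient with no PFS event (no documented progression and no death; for the sensitivity analysis, also no clinical/non-radiological progression) and no valid post-baseline tumor assessment is censored at Day 1. Death before the first scan is an event at the date of death.*

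Change the first row of Tables 20 and 21 to: *No baseline or no valid post-baseline assessment, and no PFS event as defined for that analysis.* The condition should be the absence of a PFS event, not merely being alive. A row limited to living patients would censor those with symptomatic deterioration and no scan, whom Table 21 counts as events. The condition also removes the present overlap between the first row and the death row for a patient who dies with no baseline assessment.

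The cost is one passage of text and one row in each of two tables. No new data or analysis is needed, and the PFS definition does not change.

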2.1.4 Safety endpoints

The safety analysis will be based on the reported adverse events (AE) and other safety information, such as clinical laboratory data, vital signs, ECG, weight and Eastern Cooperative Oncology Group (ECOG) performance status (PS).

Observation period

The observation period will be divided into 3 periods:

- The **pre-treatment** period is defined as the time from the signed informed consent date up to the first study treatment administration.
- The **treatment** period is defined as the time from the first study treatment administration to the last study treatment administration + 30 days.
- The **post-treatment** period is defined as the period of time starting the day after the end of the treatment period up to the end of the study.

2.1.4.1 Adverse events variables

Adverse event observation period

- Pre-treatment adverse events are defined as any adverse event reported during the pre-treatment period.
- Treatment-emergent adverse events (TEAEs) are adverse events that developed or worsened or became serious during the treatment period.
- Post-treatment adverse events are adverse events that developed or worsened or became serious during the post-treatment period.

All AEs (including SAEs and adverse events of special interest (AESI)) will be graded according to National cancer institute common terminology for adverse events (NCI-CTCAE) version 4.03 and coded to a lower-level term (LLT), preferred term (PT), high-level term (HLT), high-level group term (HLGT) and associated primary system organ class (SOC) using the version of Medical Dictionary for Regulatory Activities (MedDRA) currently in effect at Sanofi at the time of database lock.

AESI include the following terms:

- Pregnancy of female patient entered in a study as well as pregnancy occurring in a female partner of a male subject entered in a study with IMP/NIMP.
- Symptomatic overdose (serious or non-serious) with IMP/NIMP.

Primary safety endpoint for the Part 1 (predefined safety criteria):

Incidence of IMP-related predefined safety criteria during Cycle 1 and Cycle 2.

Predefined safety criteria are defined at the occurrence of any following related TEAE using NCI CTCAE v4.03:

- Grade ≥ 3 TEAE from the System Organ Class (SOC) Eyes disorders,
- Grade ≥ 3 peripheral neuropathy (Preferred Term [PT]),
- Grade ≥ 4 TEAE.

Adverse Events leading to specific analyses:

Specific analyses will be performed for the following AEs:

- Pre-specified safety criteria (cycle 1 and cycle 2).
- Corneal events (reported as AEs) as defined in the grouping GLB_CORNEAL_DISORDERS.

The last event will be identified from a grouping of adverse events based on MedDRA preferred terms.

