
ENDPOINT(S)
	
Primary endpoints:
 
Part 1
 
Safety endpoint
 
Incidence of investigational medicinal product (IMP)-related predefined safety criteria during Cycle 1 and Cycle 2.
 
Predefined safety criteria are defined as the occurrence of any following related TEAE using NCI CTCAE v4.03:
 
 • Grade ≥ 3 TEAE from the System Organ Class of eye disorders. • Grade ≥ 3 peripheral neuropathy (Preferred Term). • Grade ≥ 4 TEAE. 
Efficacy endpoint
 
Objective Response Rate, defined as the proportion of CR and PR as best response according to RECIST 1.1. Confirmation of objective responses will be performed by repeat tumor imaging (Computerized Tomography [CT] scan, Magnetic Resonance Imaging [MRI]) at least 4 weeks after the first radiological documentation of response.
 
Part 2
 
Part 2a (expansion/overexpressing CA6 cohort)
 
Objective Response Rate (see Part 1).
 
A total of 15 additional patients will be treated and the analyses performed on the whole population treated at the selected dose (Part 1 and Part 2a).
 
Part 2b (mild CA6 expression cohort)
 
Objective Response Rate (see Part 1).
 
A total of 20 patients with a mild CA6-positive membrane intensity, with at least 1% positive tumor cells at intensity $\geq 1+$ and $< 30\%$ of tumor cells at intensity of 2+, 3+, will be treated and the analyses performed.
 
Secondary endpoints (Part 1 and Part 2):
 
 • Disease control rate (DCR): number of patients with CR, PR and stable disease (SD) with a duration of at least 3 months. • Duration of Response (DOR): defined as the time from the first documentation of objective tumor response (CR or PR) to the first radiological documentation of tumor progression or death (due to any cause), whichever comes first. • Progression-free survival (PFS): defined as the time interval between the date of first study treatment administration and

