1 OVERVIEW AND INVESTIGATIONAL PLAN

1.1 STUDY DESIGN AND RANDOMIZATION

This is an open-label, multicenter, Phase II study evaluating the efficacy and safety of SAR566658 administered as a single agent via intravenous infusion in patients with CA6-positive metastatic triple negative breast cancer (TNBC) tumors after at least 1 prior chemotherapy regimen, but no more than 3 for advanced/metastatic disease.

The study will be performed in 2 parts.

Part1: Selection of the dose

Patients with metastatic TNBC overexpressing CA6 (membrane intensity of 2+, 3+ in $\geq 30\%$ of tumor cells) will be randomized to either the 90 mg/m² or the 120 mg/m² cohort, both given at Day 1 and Day 8 of each 3-week cycle. Patients randomized but not treated will be replaced. Study treatment should be initiated no later than 3 calendar days after randomization.

During treatment, safety will be monitored and the risks for predefined safety criteria during the first 2 cycles will be followed and assessed using a Bayesian binomial model. In particular, risks for overdosing and unacceptable toxicity will be assessed as soon as 4 patients treated at the dose level of 120 mg/m² become evaluable for the predefined safety criteria.

The Bayesian model assessing the rate of predefined safety criteria will use dose as a parameter. The elicitation of the prior distribution is derived from the data collected in the first in human (FIH) study (TED10499) at various dose levels and schedules of administration (190 mg/m² q3w, 240 mg/m² q3w, 90 mg/m² D1D8 q3w, and 120 mg/m² q2w).

The elicitation of the prior distribution for the two dose levels is explained in [Appendix A](#).

The decision to stop 1 arm may be taken on the basis of risk of the assessed overdosing (ie, predefined safety criteria rate above 40%) and unacceptable toxicity (ie, predefined safety criteria rate above 60%). The model recommends stopping 1 arm when its overdosing risk or unacceptable toxicity risk will not be controlled at the levels of 25% and 5%, respectively.

Simulations were performed and are presented in [Appendix A](#).

Randomization will be centralized by IVRS/IWRS, stratified on Eastern Cooperative Oncology Group (ECOG) performance status (PS) (0 versus 1). Randomization will be performed when all eligibility criteria are checked and the patient is deemed eligible. Randomization will be stopped at the end of Part 1 and the recruitment will be authorized in Part 2 only when the selected dose is chosen.

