7 LIST OF APPENDICES

- [Appendix A](#): Specification of the Bayesian design in Part 1
- [Appendix B](#): Determination of tumor response
- [Appendix C](#): Modified Response Evaluation Criteria in Solid Tumors (RECIST 1.1)
- [Appendix D](#): SOC internationally agreed order
- [Appendix E](#): Potentially clinically significant abnormalities criteria for vital signs
- [Appendix F](#): Description of primary and sensitivity analyses of PFS
- [Appendix G](#): Generic ranges for hematological and biochemistry parameters

Appendix A Specification of the Bayesian design in Part 1

Primary objective of the study:

Objectives of the study are to select the dose based on overall response rate and safety of 2 dose levels 90 mg/m² D1D8 Q3w and 120 mg/m² D1D8 Q3w.

During the part 1 of the study, 14 patients will be included in both dose levels.

Safety will be monitored and the risks for predefined safety criteria (PSC) during the first 2 cycles will be followed for patients in part 1 of the study. We will use a Bayesian binomial model as a monitoring tool.

Following predefined safety criteria have been selected for the study:

- Grade ≥ 3 TEAE from SOC eye disorders
- Grade ≥ 3 TEAE peripheral neuropathy (Preferred Term)
- Grade ≥ 4 TEAE

PSC evaluation will be performed on patients treated in the study who have completed 2 cycles, or who experienced predefined safety criteria (whatever the dose received).

The design will recommend a GO decision if it verifies overdosing risk constraints in the population:

- No more than 0.25 risk to recommend an overdosing dose (true PSC rate above 0.40).
- No more than 0.05 risk to recommend an unacceptable toxicity dose (true PSC rate above 0.60).

And so we will recommend to stop a dose level when overdosing dose or unacceptable toxicity are not controlled at the specific levels.

The Bayesian model is planned to be run after 4 evaluable patients at dose level 120 mg/m² D1D8Q3W.

The calculation will be done independently for the two tested doses 90 mg/m² D1D8Q3w and 120 mg/m² D1D8Q3W.

Assumptions for prior elicitation

Prior distribution is elicited using the data from the first in human study (TED10499).

As dose level 90 mg/m² D1D8 Q3w has been already given in the phase I study, these data will be taken into account for the prior distribution of this dose level.

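### The neuropathy component of the Part 1 safety criteria names a single Preferred Term, so a related Grade 3 neuropathy coded to another term is left out of the primary safety incidence and the Bayesian stopping model

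*SAP*

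**What the plan says.** The PSC have three components, all restricted to related events: Grade ≥3 eye events, Grade ≥3 neuropathy, and any Grade ≥4 event. The neuropathy component is worded alike in all four definitions:

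- Protocol synopsis and protocol 9.1.1: "peripheral neuropathy (Preferred Term".
- SAP 2.1.4.1: "peripheral neuropathy (Preferred Term [PT".
- SAP Appendix A, which specifies the Bayesian model: "TEAE peripheral neuropathy (Preferred Term".

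None of these gives a term list, a higher MedDRA level or a grouping for neuropathy.

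Two neighbouring definitions in SAP 2.1.4.1 are broader. The eye component is any Grade ≥3 "TEAE from the System Organ Class (SOC) Eyes disorders". Corneal events, which have their own analysis, are "Corneal events (reported as AEs) as defined in the grouping GLB_CORNEAL_DISORDERS". The SAP then says: "The last event will be identified from a grouping of adverse events based on MedDRA preferred terms". The last event in that list is the corneal one, so the grouping does not extend to the PSC.

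On the use of the count, SAP 1.1 says: "The decision to stop 1 arm may be taken on the basis of risk of the assessed overdosing". The model recommends stopping when the overdosing risk (PSC rate above 40%) or the unacceptable-toxicity risk (rate above 60%) is not "controlled at the levels of 25% and 5%, respectively".

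**The concern.** SAP 2.1.4.1 codes adverse events through five MedDRA levels, so naming the Preferred Term selects one level, and here one term. The authors evidently knew that one toxicity can spread over several Preferred Terms, because they built a grouping for corneal events. A programmer following the text would select a single term for neuropathy. A related Grade 3 neuropathy filed under another term then meets none of the three components; only at Grade 4 or above would it count.

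The PSC count is the only event input to the model. An omission can only lower the count, and so the posterior risk, which is the unsafe direction. The reported Part 1 primary safety incidence would carry the same undercount: one patient in 14 is 1/14 = 7.1 percentage points.

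**Working it through.** **Inputs (SAP Appendix A).** First-in-human PSC counts in Table 4: 1 of 17 at 90 mg/m² D1D8, and 2 of 8 at 240 mg/m² q3w, which serves as the source for 120 mg/m² D1D8. Discounts k = 0.3 and k' = 0.2. Starting prior Beta(0.5, 0.5).

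**Priors.**

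- 120 mg/m²: Beta(0.5 + 2×0.2, 0.5 + 8×0.2 − 2×0.2) = Beta(0.9, 1.7)
- 90 mg/m²: Beta(0.5 + 1×0.3, 0.5 + 17×0.3 − 1×0.3) = Beta(0.8, 5.3)

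**Rule.** With x PSC in n evaluable patients the posterior is Beta(a + x, b + n − x). Overdosing risk is 1 − F(0.40) and unacceptable-toxicity risk is 1 − F(0.60). The decision is No GO if the first exceeds 25% or the second exceeds 5%.

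**Reproducing the plan.** For 120 mg/m² at 4 patients, 1 PSC gives Beta(1.9, 4.7): 24.20% and 4.64%, GO. Two PSC give Beta(2.9, 3.7): 56.58% and 20.25%, No GO. Both match SAP Table 13. All rows of Tables 8 to 15 reproduce to within 0.005 percentage points, with the same decisions.

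**Case A: the patient with the missed event stays evaluable.** The count falls by one and n is unchanged. Each pair is overdosing risk / unacceptable-toxicity risk.

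| Dose | n | Lowest No GO count | Risks at that count | Risks one event lower | Decision becomes |
|---|---|---|---|---|---|
| 120 | 4 | 2 | 56.58% / 20.25% | 24.20% / 4.64% | GO |
| 120 | 8 | 3 | 39.52% / 6.15% | 17.26% / 1.38% | GO |
| 120 | 14 | 5 | 33.82% / 2.13% | 17.15% / 0.55% | GO |
| 90 | 4 | 3 | 41.87% / 7.34% | 18.43% / 1.67% | GO |
| 90 | 8 | 4 | 30.40% / 2.33% | 13.59% / 0.53% | GO |
| 90 | 14 | 6 | 26.96% / 0.85% | 13.63% / 0.21% | GO |

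The rows at 14 extend the same formula; the SAP tabulates decisions only up to 8 patients.

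**Case B: the patient leaves the evaluable set.** Under SAP 2.3.3 a patient without a PSC is evaluable only after 4 infusions and more than 80% of the planned dose. If the uncounted patient falls short, both x and n drop by one.

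| Dose | From | To | Risks | Decision |
|---|---|---|---|---|
| 120 | 2/4 | 1/3 | 35.18% / 9.94% | stays No GO |
| 120 | 3/8 | 2/7 | 23.98% / 2.82% | becomes GO |
| 120 | 5/14 | 4/13 | 22.39% / 1.05% | becomes GO |
| 90 | 3/4 | 2/3 | 25.64% / 3.42% | stays No GO |
| 90 | 4/8 | 3/7 | 18.46% / 1.05% | becomes GO |
| 90 | 6/14 | 5/13 | 17.68% / 0.41% | becomes GO |

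**How often?** The share of PSC events that would be missed is not in the documents. As an assumption, take shares of 0%, 10%, 25% and 50%, with all patients staying evaluable and a true PSC rate of 0.50 at 120 mg/m². The counted rate is 0.50 × (1 − share), and the chance of No GO is the binomial probability of reaching the boundary:

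- n = 4, at least 2 counted: 68.8%, 60.9%, 48.1%, 26.2%
- n = 8, at least 3 counted: 85.5%, 78.0%, 63.0%, 32.1%

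The missed share cannot exceed the share of PSC that are Grade 3 neuropathy, so 50% is an outer case and 0% is possible.

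**The case against.** The strongest reply is that the mechanism is unproven. The documents do not list MedDRA terms or say how neuropathy reports would be coded, and the Preferred Term label may have been meant loosely, for the medical concept. The figures above also show only that one event matters at a boundary, as it would in any rule based on 4 or 8 patients. All of this is fair, and it limits what can be said about size. It does not remove the point: no section says the label is loose, and if a broader concept was meant the text still needs correcting.

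Four stronger readings are tempting and are not supported.

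- *Such neuropathies would be ignored in dose selection.* The end-of-Part-1 criteria (synopsis, protocol 6.3, SAP 1.1) consider peripheral neuropathy with no term limit, and adverse events leading to dose reduction or discontinuation. Protocol Table 3 attaches a delay and a dose reduction or withdrawal to Grade 3 neuropathy, so these events should surface there. Neuropathy also has its own analysis in SAP 2.4.5.1. That review, however, comes after all 14 patients per arm are treated, whereas the model monitors during treatment.
- *The model stops an arm by itself.* It recommends; the decision may be taken on that basis.
- *The 32% neuropathy figure in protocol 4.1.2 measures the events at risk.* It is not limited to Grade ≥3, to related events or to Cycles 1 and 2, and it refers to the 89 patients at the doses of interest, not all 114 enrolled. It shows only that neuropathy is an expected toxicity.
- *One missed event always reverses the decision.* It does so only at a boundary count, and not at the 4-patient look if the patient leaves the evaluable set.

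**Conclusion.** The point holds in a limited form. If the stated rule is followed, a related Grade 3 neuropathy coded outside the one named Preferred Term is missing from the primary safety incidence and from the model. The error can only go in the unsafe direction.

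Its frequency is unknown. At a boundary, one such event turns No GO into GO at 4, 8 and 14 patients for both doses if the patient stays evaluable. If the patient does not, the change occurs at 8 and 14 but not at 4. These results rest on the SAP's own priors, discounts and limits, and on reading the Preferred Term label literally.

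The documents do not say whether the counts in Table 4 used the same single term; if they did, the priors could be low for the same reason. This should be corrected, but it does not undermine the design: the stopping limits are unaffected and other reviews would see the events.

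**What to change.** In the protocol synopsis, protocol 9.1.1, SAP 2.1.4.1 and SAP Appendix A, replace the single Preferred Term with a named, pre-specified grouping of neuropathy terms, built as for GLB_CORNEAL_DISORDERS and fixed before the first model run. Changing only some of the four would leave conflicting definitions. Use the same grouping for the neuropathy analysis in SAP 2.4.5.1, which has no term list. If one term is truly intended, say so and justify it.

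Check the first-in-human counts in SAP Table 4 (1 of 17 and 2 of 8) on the same grouping, so that prior and new data count the same events. Only if those counts change do the priors, the choice of k and k', and Tables 6 to 15 need to be re-run.

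The cost is a term list, four short text changes and possibly that re-run. The PSC rate can only stay the same or rise, so a No GO may become somewhat more likely. No threshold, dose or clinical rule changes.
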